## List of Abbreviations

ABMUHB	Abertawe Bro Morgannwg Health Board
CAD-CAM	Computer aided design – Computer aided manufacture
CMF	Cranio-maxillo-facial (surgery)
CBCT	Cone-beam computer tomography (dental)
CT	Computer tomography (medical)
H&N	Head & Neck (surgery)
HRQOL	Health related quality of life
ORN	Osteoradionecrosis (of the mandible)
PI	Principal investigator
PSI	Patient-specific implant
SLM	Selective laser melting
3D	Three-dimensional

## 2.0 Literature Review and Study Rationale

### 2.1 Introduction / context

Head and neck (H&N) cancer includes cancers originating from various (and often overlapping) sub-sites in the head and neck region (including the oral cavity, pharynx, larynx, nose and paranasal sinuses). H&N cancer is the eighth most common cancer in the UK (2014). In the UK (mainland) it is four times commoner in men than women, and geographically European age-standardised (AS) incidence rates are higher in males in Wales than England (with rates highest in Scotland overall for both sexes). H&N cancer incidence has increased in both sexes since the 1990s with a greater percentage increase amongst females, closing the gender difference in incidence over time. (Cancer\_Research\_UK)

For head and neck cancer in general, late stage disease is a commoner presentation than early stage disease (62% are stage III/IV at presentation

versus 38% at stage I/II).(NICR, 2016) Consequently, major resective surgery, aiming for cure (with immediate reconstruction for optimal functional outcome) is commonplace. In the case of oral cancer specifically, advanced tumours frequently involve the mandible (lower jaw bone), requiring resection/removal of part of the mandible to a variable extent, depending on the nature of the tumour (with/without postoperative radiotherapy, depending upon patient and tumour-specific factors).

Radiotherapy is commonly used in head and neck cancer in isolation (as an alternative to surgery), most commonly for laryngeal and tongue base tumours as it helps to preserve natural speech and swallowing. However for advanced squamous cell carcinomas (SCCs), combined treatment modalities (surgery and radiotherapy / chemotherapy and radiotherapy) offer the highest chance of cure.(Nutting, 2016) For patients in whom radiotherapy is used, there is an additional lifelong risk of developing osteoradionecrosis (ORN) of the mandible as a side-effect. Osteoradionecrosis is in effect, "hypovascularity and necrosis of bone followed by trauma-induced or spontaneous mucosal breakdown, leading to a non-healing wound."(Butterworth et al., 2016) In the latter stages of the disease process, ORN can result in pathological fracture of the mandible and/or an orocutaneous fistula, requiring free tissue transfer to repair the defect.(Lyons and Brennan, 2014) Consequently, in the context of managing head and neck cancer, mandibular reconstruction with titanium plates and free tissue transfer is commonly performed; not only for immediate reconstruction after surgical resection of advanced tumours, but also for treatment of late-stage ORN. Furthermore, similar techniques can be used for extensive and progressive (but histologically benign) jaw tumours.

Choice of reconstructive technique for mandibular defects depends on the amount of bone to be resected.(Brown et al., 2016) However, in larger defects, it is felt by many surgeons that the gold standard for mandibular reconstruction is a fibula free flap (autologous vascularized bone and soft tissue, transplanted from the leg and anastomosed to an arteriovenous supply in the neck) supported within an osseosynthesis plate to facilitate primary bony union/healing.(Kokosis et al., 2016) Other choices of bony free-flaps can be used such as the deep circumflex iliac artery (DCIA) flap, favoured over the fibula free flap by some authors.(Chen et al., 2014) Most osseosynthesis plates used for this purpose are composed of titanium, because of its intrinsic biocompatibility and high strength-to-weight ratio.(Parthasarathy, 2014). Traditionally, titanium was flexed or moulded intraoperatively by eye (during surgery) to reconstruct mandibular defects, without the modern benefits of preoperative 3D computer-aided planning. The process of flexing a rigid osseosynthesis plate for mandibular reconstruction inherently contributes to the overall duration of the surgery, is dependent upon the experience and skill of the surgeon and carries the risk of human error in dimensional accuracy of the reconstruction, simply because it is done 'by hand and by eye'. Furthermore, manually deforming titanium implants in this manner creates intrinsic stresses within the implanted material, potentially weakening the overall reconstruction in the long term whilst subjected to cyclical loading forces from mastication/chewing for example.(Park et al., 2016)

## **2.2 Computer aided 3D planning and customisation of mandibular reconstruction osseosynthesis plates**

Three dimensional (3D) planning and virtual surgery has evolved in recent years and it is postulated that it improves efficiency, accuracy, creativity and reproducibility in CMF surgery in particular.(Steinbacher, 2015) Rapid prototyping is a process by which a stereolithographic resin model can be produced following collection of data from 3D imaging such as computer tomography (CT) scanning. The process of virtual surgery (following analysis of 3D imaging data) provides the means to rapid-prototype a stereolithographic resin model/mould upon which a titanium implant can be flexed, pressed or moulded preoperatively (and most importantly, checked against the stereolithographic model) for subsequent intraoperative use. This technique has become commonplace in UK maxillofacial centres. When compared to traditional intraoperative shaping techniques, it improves accuracy and efficiency in mandibular reconstruction (notably eliminating the time taken during surgery to bend the plate by eye that would otherwise be required using the traditional approach, yet allowing as much time as needed by the technician preoperatively to achieve the best 'handmade' result possible).(Gil et al., 2015) Nevertheless, this type of 'customisation' still remains open to considerable inaccuracies/human errors of the technician in flexing the plate by hand. Furthermore the risk of introducing mechanical weaknesses by flexing the plate remains.

Besides producing patient-specific implants (PSIs), 3D planning and virtual surgery facilitates the production of intraoperative surgical cutting and drilling guides/'stents', which improve accuracy of bone cuts (osteotomies) in mandibular reconstruction with fibula free flaps and aids precise placement of osseointegrated dental implants (Wang et al., 2016, Allum, 2008).

## **2.3 3D printing in mandibular reconstruction**

It is clear that to date, 3D CAD-CAM has improved the accuracy of mandibular reconstructions in head & neck oncology surgery. With the advent of "3D printing" (more specifically selective laser melting; SLM), it has been proposed by one author group that laser sintered mandibular reconstruction plates reduce the duration of surgery and frequency of complications, as well as producing a more accurate reconstruction due to the elimination of human error in the final stages of fabrication (in contrast to the "pre-flexing to a rapid-prototyped stereolithographic model" approach). The authors suggest that further randomized studies would be useful to determine whether CAD-CAM mandibular reconstruction is economically sustainable in maxillofacial oncology surgery (Tarsitano et al., 2016). Currently a team in Hong Kong are prospectively evaluating clinical outcomes and complications of laser sintered mandibular reconstruction plates in a proposed series of 48 patients (Su, 2017). However, to date there are no randomized trials comparing clinical and

economic outcomes in 3D-printed mandibular reconstruction plates and cutting guides versus manually pre-flexed plate techniques.

## 2.4 Summary

In summary, 3D printing (SLM) of titanium provides an opportunity to negate the impact of human error in customisation of mandibular reconstruction osseosynthesis plates and alignment of osteotomies, potentially improving upon the predictability and precision of mandibular reconstruction in head & neck cancer patients. However, with a lack of high-level evidence to date, there is no clear consensus on whether the SLM approach provides a better treatment solution when compared to other more established, but potentially more crude techniques of plate customization (pre-flexing to a rapid prototyped model). Consequently a situation of clinical equipoise exists and in this context, warrants a well-designed observational study to evaluate any differences between the two treatment approaches.

# 3.0 Study aims and objectives

## 3.1 Primary outcome

Primarily, the study aims to evaluate:

1. Predictability and resultant dimensional accuracy of mandibular reconstructions performed using:
  - Fibular free-flap reconstruction of the mandible with a customized pre-flexed mandibular reconstruction plate and cutting guides (Treatment pathway A)

OR

1. Fibular free-flap reconstruction of the mandible with a customized SLM mandibular reconstruction plate and cutting guides (Treatment pathway B)

## 3.2 Secondary outcomes

Secondarily, the study aims to compare treatment pathways A and B for:

2. The duration of surgery (in particular individual components of the surgery such as flap warm ischaemia time, duration of osteotomies and plate fixation procedures.

3. The operators' perceptions of the overall intraoperative usability, confidence with the technique and immediate satisfaction of the surgical result.
4. The need to make minor adjustments to either the plate, osteotomy or screw holes in order to fit the plate during surgery.
5. Incidence of postoperative complications (as recorded during inpatient stay as well as at 6 weeks, 6 months and 1 year outpatient follow up visits), for example:
  - a. Localised infection
  - b. Plate extrusion/exposure
  - c. Length of hospital stay (including duration of intensive care / high-dependency / ward requirements)
  - d. Mal / non / delayed-union of the bony components of the mandibular reconstruction (from objective analysis of clinically routine postoperative CT scan imaging)
  - e. Plate fractures/failures
6. Medium-term (up to 1 year) functional outcomes, for example:
  - a. Feasibility of dental implant rehabilitation (specifically in the technical context of clinical and/or radiological perspective of bone quality and anatomy as well as in the holistic context of the patient's suitability overall, in order to determine the importance of reconstructed bony anatomy in the decision processes and planning of dental rehabilitation)
  - b. Objective evaluation of changes in dental occlusion (with the aid of dental model analysis).
  - c. Objective assessment of changes in facial aesthetics (facial symmetry based upon baseline and postoperative 3D photography (stereophotogrammetry).
7. Patient-perceived quality of life:
  - a. using a validated quality of life assessment tools:
    - i. University of Washington Quality of Life Questionnaire v4
    - ii. Short-form Derriford appearance scale (DAS24)
    - iii. Liverpool oral rehabilitation questionnaire
  - b. by time to return to work / social status at 1 year (where applicable)
8. Economic implications (with economic analysis taking the above clinical and social outcomes into account).

## 4.0 Study design

JaW PrinT is a 'real-world' prospective observational pilot study, evaluating the clinical effectiveness, usability and economics of two approaches to mandibular reconstruction surgery (figure 1). Patient participants will be recruited prospectively over a minimum period of 18 months (with observation of at least 10 participants in each treatment pathway). The figures are based upon the historical clinical practice of the research site, with both techniques in equal use;

choice depending on resources, surgical training requirements and surgeon's clinical preference.

As a purely observational study, treatment choice will be made in the normal clinical manner and will in no way be influenced by the study itself.

Participants will be followed up at their routine outpatient clinics (6 weeks, 6 months and 1 year postoperatively) with prospective outcomes data collection (figure 1).

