**Preoperative baseline data collection (CRF01 form).**

- Medical history and screening of comorbidities (including comorbidity score & performance status), smoking and alcohol status.
- Evaluate for history of any previous radiotherapy treatment (date started and completed, regime details).
- Physical assessment (BMI, oral hygiene status).
- Detailed social history
- University of Washington QoL Questionnaire v4.
- Short-form Derriford appearance scale (DAS24).
- Liverpool oral rehabilitation questionnaire.
- 3D Photograph (Stereophotogrammetry) of the head and neck
- Baseline clinical blood tests (FBC, U&E, Clotting screen)

**Treatment allocated in normal clinical manner by surgeon to either pathway A (surgery with pre-flexed plate) or pathway B (surgery with SLM plate).**

Participant blinded to treatment allocation at this stage

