**Perioperative / inpatient data collection (CRF02 form).**

- Prior to commencing surgery, bite registration to be obtained (using viscoelastic silicone impression putty)
- At surgery, record of:
  - Times at which mandibular osteotomies are first started (cutting guides first placed onto mandible) and completed
  - Time of knife-to-skin for flap harvest
  - Time of flap detachment
  - Time of completing fixation of the plate (with flap) in its final resting position (i.e. when completion of fixation to the residual mandible)
  - Time of completing arterial anastomosis
- Record of need for any intraoperative adjustment to the plate, osteotomies and/or planned drill hole positions.
- Surgeon rating of usability, confidence of use, satisfaction with reconstructive procedure.
- Scrub nurse rating of usability, confidence of use, satisfaction with reconstructive procedure.
- Record of days-stayed on ITU / HDU and/or Ward, date of discharge.
- Record of all complications as inpatient (peri & post operative).

**6 weeks follow up** (CRF03 form).

- Physical assessment (BMI, oral hygiene status).
- University of Washington QoL questionnaire.
- Short-form Derriford appearance scale (DAS24).
- Liverpool oral rehabilitation questionnaire.
- Report on complications.
- 3D Photograph (Stereophotogrammetry) of the head and neck.
- Detailed social history (e.g. current occupation / employment)

**6 months follow up** (CRF04 form).

- Data recorded as per CRF03 form.
- Postoperative CT mandible scan (evaluation of actual vs. planned dimensions, quantitative evaluation of bony cortical union at osteotomy sites)

**1 year follow up** (CRF05 form).

- Data recorded as per CRF03 form.
- Dental assessment (including routine cone beam CT scan) and restorative dentist rating of technical and practical feasibility of prosthetic rehabilitation options

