#### **4.4 Treatment pathway allocation**

Upon recruitment, provision of informed consent and collection of baseline data, as per standard clinical practice, the patient participant's CT scan data is used to produce a virtual surgical plan for the mandibular resection and fibular free-flap reconstruction. Once the clinically optimal reconstructive surgical plan is established by the surgeon and technician, the choice of surgical approach will be made in the routine clinical manner by the surgeon: Pathway A (pre-flexed customized mandibular reconstruction plate and cutting guides) or to pathway B (SLM customized mandibular reconstruction plate and cutting guides). Both

treatment pathways are already part of routine/standard clinical practice at ABMUHB.

The expected/planned patient numbers for this study are based upon the historical workload of the Oral and Maxillofacial Surgery department at Abertawe Bro Morgannwg University Health Board (ABMUHB) of 10-20 cases annually. A recruitment period of 18 months with follow-up for 1 year fits within the time constraints of the postgraduate student investigator's PhD timeline.

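### The listed data include neither the operator nor the reason for pathway choice, so the learning-curve aim and the A-versus-B comparisons of times, adjustments and surgeon ratings cannot be interpreted from them

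*Protocol*

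**What the plan says.** Protocol section 4.0 presents an observational pilot with at least 10 participants per pathway. It describes allocation between the two techniques as "choice depending on resources, surgical training requirements" and the surgeon's clinical preference. Section 4.4 places the decision after consent, baseline data and the virtual plan: "the choice of surgical approach will be made in the routine clinical manner by the surgeon". Figure 1 agrees: "Treatment allocated in normal clinical manner by surgeon to either pathway A" or to pathway B.

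The purpose is partly comparative. Section 2.4 says that the state of evidence "warrants a well-designed observational study to evaluate any differences between the two treatment approaches". Section 3.2 opens with "Secondarily, the study aims to compare treatment pathways A and B for" and lists, as items 2 to 4, duration of surgery and its components, the operators' perceptions, and the need for minor adjustments during surgery.

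The perioperative list in Figure 1 (CRF02) includes "Surgeon rating of usability, confidence of use, satisfaction with reconstructive procedure", with the same rating from the scrub nurse. Section 4.5.2 adds that the ratings also serve to evaluate a possible learning-curve effect.

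The baseline lists (Figure 1 and section 4.5.1) cover patient factors. The perioperative lists (Figure 1 and section 4.5.2) cover timings, adjustments, ratings, length of stay and complications. The follow-up lists (Figure 1, both sections numbered 4.5.3, and section 4.5.4) cover outcomes. None of them names the operating surgeon, grade, previous cases with the technique, or the reason for choosing A or B.

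**The concern.** The three drivers that section 4.0 names are not patient characteristics, so the baseline variables do not capture them. Training needs and surgeon's preference bear directly on who operates and how practised that person is with the technique. Operating time, the need for adjustments and the surgeon's own ratings are the outcomes most likely to respond to that.

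If one pathway were used more often by less experienced operators, or chosen more often by its enthusiasts, a difference on these outcomes could partly reflect that and not the plate. A reader of the results would have no table from which to judge it.

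The learning-curve aim has the same problem in a more direct form. A rating has to be tied to a surgeon and to that surgeon's experience before it says anything about learning.

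**Working it through.** The protocol gives no sample size calculation or operator data, so there is no figure to reproduce. The check is a comparison of sections, followed by simple counts.

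**1. Stated drivers against listed data**

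| Item named or needed | Where it arises | In the listed data? |
|---|---|---|
| Reason for choice (resources, training, preference) | Section 4.0 | No |
| Operating surgeon | Sections 4.0 and 4.5.2 | No |
| Grade | Section 4.0 (training) | No |
| Prior cases with the technique | Section 4.5.2 (learning curve) | No |
| Order of cases within the study | Section 4.5.2 (learning curve) | Probably recoverable from the dates of stay in section 4.5.2 |

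Case order alone gives a trend for the department. It does not place a rating on any one surgeon's curve. Section 4.4 says both techniques are already in routine use, so operators may enter the study with different amounts of experience.

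**2. Timing of the missing items**

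Section 4.4 puts the choice after the following: "Upon recruitment, provision of informed consent and collection of baseline data". The reason for choice therefore cannot sit on CRF01, which is completed earlier. It belongs on CRF02 or on a form completed at the moment of choice.

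**3. Expected numbers**

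Inputs: a workload "of 10-20 cases annually" (section 4.4), an 18-month minimum recruitment period and equal historical use of the techniques (section 4.0). The counts assume that every case is eligible and consents.

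- Cases: 10 × 1.5 = 15, and 20 × 1.5 = 30.
- Per pathway at equal use: 15 / 2 = 7.5, and 30 / 2 = 15.
- The stated minimum of 10 per pathway gives 20 in total.

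**4. What the extra data could support**

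- Four categories of reason × 2 pathways = 8 cells.
- Average per cell: 20 / 8 = 2.5, and 30 / 8 = 3.75 (about 3.8).

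This is enough for a table but not for a model.

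**5. Precision of an unadjusted comparison, for scale**

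The 95% half-width for a difference in means, in SD units, is t × √(2/n), assuming equal SDs and a continuous outcome.

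- n = 10 per pathway: t(0.975, 18) × √(2/10) = 2.101 × 0.447 = 0.94 SD.
- n = 15 per pathway: t(0.975, 28) × √(2/15) = 0.75 SD.

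The comparisons are imprecise even without any operator effect, which is a further reason to present them as descriptive.

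**6. Size of any bias**

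It would be the difference between pathways in operator mix multiplied by the effect of operator on the outcome. The protocol gives neither quantity, so no figure is offered.

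**The case against.** The strongest reply is that silence in these lists proves little, because they are plainly not exhaustive. Serum albumin is in section 4.5.1 but not in Figure 1. Overall operating time is in section 4.5.2 but not in Figure 1. Social history at 6 weeks is in Figure 1 but not in the 6-week section, and wound healing is the reverse. An operator field could well exist on CRF02. This stands, and it makes checking the forms the first step.

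A second reply is that the gap can partly be repaired later. Section 7.0 keeps clinical records at the site and has the team audit data collection quarterly. With some 15 to 30 cases at one site, operator and grade might be traced and the surgeon asked for the reason. This also stands: a reader might infer that no later analysis plan could tabulate the reason for choice, but that goes too far. Retrospective answers would be less reliable than an entry made at the time, and no more than that can be said.

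A third reply concerns scope. A reader might infer that every secondary comparison is undermined. The documents do not support that. The link runs from operator and technique choice to times, adjustments and surgeon ratings. Nothing in the protocol shows how the stated drivers would distort complications, dental feasibility, quality of life or cost. Patient factors are collected, and section 6.0 plans regression.

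Finally, surgeon choice is the declared design of an observational pilot and is not a fault. The protocol does not give the number of surgeons, and if one surgeon led every case there would be no imbalance in operator identity. A reader might infer a known or large bias, and the documents give no basis for that.

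**Conclusion.** The point holds for the learning-curve aim in section 4.5.2 and for items 2 to 4 of section 3.2. From the data the protocol lists, the first cannot be met, and the A-versus-B differences in the second cannot be separated from who operated and why that technique was chosen. Description of reconstructive accuracy within each pathway is not affected, and the scrub nurse ratings offer a partial check on the surgeons' own.

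The conclusion rests on one assumption: that the unseen case report forms do not already hold these items. The size of any bias is unknown, and imbalance is possible but not shown. It ranks as a cheap improvement, not a flaw that invalidates the study. It is worth acting on while cases are being done, because the reason for choice is recorded most reliably when the choice is made.

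**What to change.** Check the case report forms first. If the items are absent, add four fields to CRF02 or to a short form completed when the pathway is chosen:

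- reason for choosing A or B (resources / training / preference / other);
- coded operating surgeon;
- that surgeon's grade;
- that surgeon's prior case count with the technique.

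Tabulate these by pathway. Show operating times, adjustments and surgeon ratings by operator and case order, and present the A-versus-B comparisons of those three outcomes as descriptive. At about 10 patients per pathway, any adjusted estimate should be no more than an optional sensitivity analysis.

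The cost is 4 × 20 = 80 to 4 × 30 = 120 short entries, all known to the team at the time. Treatment choice is untouched. The drawbacks are a little extra form-filling and small cells, and the comparison stays observational whatever is recorded.
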